6.4. Electrocardiogram

ECG variables that will be analyzed include heart rate, RR, PR interval, QRS interval, QT interval and QTc intervals. The corrected QT (QTc) intervals will include QTcB (Bazett) and QTcF (Fridericia). Baseline values are defined in Section 2.2.

The maximum postbaseline value during each treatment phase (induction and optimization/maintenance phase) will be presented separately and will be computed for each ECG parameter using data from both scheduled and unscheduled visits.

Summary tables for observed values and changes from baseline will be presented at each scheduled time point during both treatment phases (induction and optimization/maintenance phases).

The frequency of treatment-emergent abnormalities will be tabulated and presented for all treatment phases. The identification of treatment-emergent abnormal ECG values is based on the post-baseline value (a value occurring after the start of the phase) being out of range while the Baseline value (described in Section 2.2) is either missing or within the limits given in Table 5. If postbaseline ECG results are above the upper limits (abnormally high) and the Baseline value is below the lower limits (abnormally low) or missing, then the postbaseline abnormality will also be considered treatment-emergent. The same applies to the postbaseline value being below the lower limits (abnormally low) with the Baseline value being above the upper limits (abnormally high) or missing. Abnormal ranges for the HR, PR, QRS and QT intervals are given in Table 5.

Table 5: Limits for HR, PR, QRS and QT Interval Abnormality

ECG parameter	Abnormally Low	Abnormally High
HR (bpm)	≤ 50	≥ 100
PR interval (msec)	--	≥ 210
QRS interval (msec)	≤ 50	≥ 120
QT interval (msec)	≤ 200	≥ 500

Based on the maximum QTc value for each subject during a given phase (separate for each QTc correction, QTcB and QTcF) the incidence of abnormal QTc values and changes from Baseline will be summarized. Criteria for abnormal corrected QT intervals and changes from Baseline are given in Table 6 and are derived from the International Conference on Harmonization (ICH) E14 Guidance⁴ (the same criteria apply to all QT corrections).

Table 6: Criteria for Abnormal QTc Values and Changes From Baseline

Parameter	Classification	Criteria
Clinically Significant QTc Value	No	≤ 500
	Yes	> 500
QTc change from Baseline ^a	No concern	≤ 30
	Concern	> 30 – 60
	Clear concern	> 60
QTc value	Normal	≤ 450
	> 450 - 480	> 450 - ≤ 480
	> 480 - 500	> 480 - ≤ 500
	> 500	> 500

These criteria are based on ICH E14 Guideline

^a Baseline is defined in Section 2.2.

The proportion of subjects with treatment emergent abnormalities will be presented for the IND and OP/MA phases. A listing of subjects with abnormalities will also be provided.

6.5. Nasal Examination

Targeted nasal examinations (including the upper respiratory tract/throat) will be conducted by a qualified healthcare practitioner. The objective of the examination at Screening is to rule out any subjects with anatomical or medical conditions that may impede drug delivery or absorption.

Subsequent examinations will consist of a visual inspection of the nostrils, nasal mucosa, and throat for nasal erythema, rhinorrhea, rhinitis, capillary/blood vessel disruption and epistaxis and graded as follows: absent, mild, moderate, or severe.

Changes in findings from Baseline (described in Section 2.2) for each examination (including the upper respiratory tract/throat) will be listed for each treatment phase.

6.6. Other Safety Parameters

6.6.1. Columbia-Suicide Severity Rating Scale (C-SSRS)

The C-SSRS⁷ is a low-burden measure of the spectrum of suicidal ideation and behavior that was developed in the National Institute of Mental Health Treatment of Adolescent Suicide Attempters Study to assess severity and track suicidal events through any treatment. It is a semi structured clinician-administered questionnaire designed to solicit the occurrence, severity, and frequency of suicide-related ideation and behaviors during the assessment period. Using the C-SSRS, potentially suicide-related events will be categorized using the following scores:

Suicidal Ideation (1-5)

- 1: Wish to be Dead
- 2: Non-specific Active Suicidal Thoughts
- 3: Active Suicidal Ideation with Any Methods (Not Plan) without Intent to Act
- 4: Active Suicidal Ideation with Some Intent to Act, without Specific Plan
- 5: Active Suicidal Ideation with Specific Plan and Intent

Suicidal Behavior (6-10)

- 6: Preparatory Acts or Behavior
- 7: Aborted Attempt
- 8: Interrupted Attempt
- 9: Actual Attempt (non-fatal)
- 10: Completed Suicide

If no events qualify for a score of 1 to 10, a score of 0 will be assigned (0 = “no event that can be assessed on the basis of C-SSRS”). Higher scores indicate greater severity.

The summaries of the C-SSRS outcomes will be based on the Full analysis set for subjects who have at least 1 post-baseline C-SSRS measurement and a pre-treatment C-SSRS assessment.

A frequency distribution at each scheduled time point will be provided. Shifts from the Baseline value (described in Section 2.2) to the most severe/maximum score during each phase will be summarized.

The maximum score assigned for each subject will also be summarized into one of three broad categories: No suicidal ideation or behavior (0), Suicidal ideation (1 - 5), Suicidal behavior (6 - 10). Shifts from the Baseline value (described in Section 2.2) to the maximum category during each phase will be summarized.

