The C-SSRS is a measure of the spectrum of suicidal ideation and behavior that was developed in the National Institute of Mental Health Treatment of Adolescent Suicide Attempters Study to assess severity and track suicidal events through any treatment.⁵⁸ It is a clinical interview providing a summary of both suicidal ideation and behavior that can be administered during any evaluation or risk assessment to identify the level and type of suicidality present. The C-SSRS can also be used during treatment to monitor for clinical worsening.

The C-SSRS assessments in this study will use the Since Last Visit version, which will assess suicidal ideation and behavior since the subject's last visit.

Modified Observer's Assessment of Alertness/Sedation (MOAA/S)

The MOAA/S will be used to measure treatment-emergent sedation, with correlation to levels of sedation defined by the American Society of Anesthesiologists (ASA) continuum.

The MOAA/S scores range from 0=no response to painful stimulus (corresponds to ASA continuum for general anesthesia) to 5=readily responds to name spoken in normal tone (awake; corresponds to ASA continuum for minimal sedation).

On specified days in the T&E, the MOAA/S will be performed every 15 minutes from predose to $t=+1$ hours postdose.

- If the score is ≤ 3 at any time during the 1 hour postdose interval, the MOAA/S will be performed every 5 minutes until a score of 4 is reached (at which point a frequency of every 15 minutes can be resumed until $t=+1$ hours post dose).
- If a subject does not have a score of at least 5 at $t=+1$ hours postdose, they should continue to be monitored. For subjects with a score of 4, the assessment should be repeated every 15 minutes. And for subjects with a score of ≤ 3 , the assessment should be repeated every 5 minutes until the score returns to 5 or the subject is referred for appropriate medical care, if clinically indicated.

Clinical Global Assessment of Discharge Readiness (CGADR)

The CGADR will be used to measure the subject's current clinical status and is the clinician's assessment of the readiness to be discharged from the study site.

The clinician will answer “Yes” or “No” to the question “*Is the subject considered ready to be discharged based on their overall clinical status (eg, sedation, blood pressure, and other adverse events)?*”

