Laboratory data will be summarized by type of laboratory test. Markedly abnormal results (specified in the SAP) will be used in the summary of laboratory data. Descriptive statistics will be provided for each laboratory analyte at baseline and at each scheduled time point in each phase of the study. Changes from baseline results will be presented. Frequency tabulations of the abnormalities will be provided. Listings of subjects with markedly abnormal laboratory results will also be provided.

Electrocardiogram (ECG)

The effects on cardiovascular variables will be evaluated by means of descriptive statistics and frequency tabulations. These tables will include observed values and changes from baseline values.

Electrocardiogram data will be summarized by ECG parameter. Descriptive statistics will be calculated at baseline and for observed values and changes from baseline at each scheduled time point. Frequency tabulations of the abnormalities will be made.

The ECG variables that will be analyzed are heart rate, PR interval, QRS interval, QT interval, and QT interval corrected (QTc) according to Bazett's formula (QTcB) and Fridericia's formula (QTcF).^{3,65}

Descriptive statistics of QTc intervals and changes from baseline will be summarized at each scheduled time point. The percentage of subjects with QTc interval >450 msec, >480 msec, or >500 msec will be summarized, as will the percentage of subjects with QTc interval increases from baseline <30 msec, 30 to 60 msec, or >60 msec.

All important abnormalities in ECG waveform that are changes from the baseline readings will be reported (eg, changes in T-wave morphology or the occurrence of U-waves).

C-SSRS

Suicide-related thoughts and behaviors based on the C-SSRS will be summarized in incidence and shift tables. Separate endpoints for suicidal ideation and suicidal behavior will be defined and summarized descriptively.

Other Safety and Tolerability Questionnaires and Assessments

CGDAR and MOAA/S: Descriptive statistics of scores and their changes (and/or percent changes) from pre-dose or baseline will be summarized at each scheduled time point.

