1.1. Trial Objectives

Primary Objectives

The primary objective of this study is to assess the safety and tolerability of intranasal esketamine in subjects with Treatment Resistant Depression (TRD), with special attention to the following:

- Potential long term effects on cognitive function
- Treatment-emergent adverse events (TEAEs), including TEAEs of special interest
- Post dose effects on heart rate, blood pressure, respiratory rate and blood oxygen saturation
- Potential effects on suicidal ideation/behavior

Secondary Objective

The secondary objective is to assess long-term efficacy, including effects on:

- Depressive symptoms (clinician and self-reported),
- Overall severity of depressive illness,
- Functioning and associated disability,
- Health-related quality of life and health status,

Exploratory Objectives

The exploratory objectives are to assess:

- Medical resource utilization
- Response and remission rates to a second induction phase in eligible subjects who had relapsed in study ESKETINTRD3003
- Subject treatment satisfaction
- Subject tradeoff preferences for key benefit and harm outcomes associated with TRD treatment, using a stated-choice preference survey

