6.2. Clinical Laboratory Tests

Descriptive statistics (N, mean, median, minimum, and maximum) for values and changes from baseline will be provided for clinical laboratory tests (hematology, chemistry and urinalysis) at each scheduled time point in the IND and OP/MA phases. Baseline values (as described in Section 2.2) will be used for change summaries and to determine abnormal values during all treatment phases.

Clinical laboratory tests that meet the criteria for markedly abnormal will be listed by subject for each phase. The incidence of treatment-emergent markedly abnormal (TEMA) laboratory values that occurred at any time during each treatment phase will be presented. Clinical laboratory test values will be considered “TEMA using the criteria defined by the Sponsor (Janssen Research & Development, LLC)” listed in Attachment 1. The identification of TEMA laboratory values is based on the postbaseline value being out of range while the baseline value (defined above) is either missing or within the range given in Attachment 1. If postbaseline laboratory results are above the upper limit and the baseline value is below the lower limit, then the post-baseline abnormality will also be considered TEMA. The same applies to the postbaseline value being below the lower limit with the baseline value being above the upper limit. Baseline values are defined in Section 2.2.

The incidence of subjects with ALT values $> 3 \times$ upper normal limit (ULN) will be presented for each study phase. Additionally, incidence of hepatic toxicity (Hy’s Law)⁹ defined as ALT values $> 3 \times$ ULN and total bilirubin values $> 2 \times$ ULN will be presented for each study phase. Similar to the markedly abnormal analysis, only subjects with Baseline ALT values $\leq 3 \times$ ULN (and Baseline total bilirubin values $\leq 2 \times$ ULN for hepatic toxicity) (or if the Baseline value is missing) will be eligible for these analyses.

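### SAP 6.6.1 requires a pre-treatment C-SSRS for every C-SSRS summary, although only the shift tables need one

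*SAP*

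**What the plan says.** Suicidality is one of the items singled out in the primary objective: "Potential effects on suicidal ideation/behavior" (SAP 1.1; Protocol 2.1.1 has the same item). Protocol 11.3 describes the analysis in one line: "Suicide-related thoughts and behaviors based on the C-SSRS will be summarized in incidence and shift tables". It attaches no condition about forms.

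SAP 6.6.1 adds a condition. It takes the Full analysis set and narrows it to those "for subjects who have at least 1 post-baseline C-SSRS measurement and a pre-treatment C-SSRS assessment". No output is exempted. Three kinds of output follow:

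- by visit: "A frequency distribution at each scheduled time point will be provided";
- by subject: "The maximum score assigned for each subject will also be summarized into one of three broad categories" (none, ideation 1 to 5, behavior 6 to 10);
- shifts from baseline to the worst score and to the worst category in each phase.

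The top of the scale is "10: Completed Suicide". Protocol 9.2 describes how the instrument is administered: "It is a clinical interview providing a summary of both suicidal ideation and behavior", in its Since Last Visit version.

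**The concern.** A shift table cannot be filled without a baseline, so the condition is natural there. A count of subjects with ideation at a visit, or of subjects whose worst post-baseline category was behavior, uses post-baseline data only. Requiring a pre-treatment form for those outputs discards observed suicidal ideation or behavior for a reason unrelated to what is being counted. In a single-arm safety extension with a stated interest in suicidality, these are the tables a reader would use for incidence. Behavior events may be few, so losing even one could be noticeable.

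**Working it through.** No formula in the plan applies. The study has no hypothesis and no sample-size calculation, and it gives no figure for missing forms. The check compares the rules and then applies the 6.6.1 rule to each kind of subject.

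**Rules side by side**

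| Source | Output | Treatment of a missing baseline |
|---|---|---|
| SAP 2.4 and 2.4.2 | change-from-baseline analyses | subject excluded |
| SAP 6.2 | markedly abnormal laboratory values | eligible: baseline "is either missing or within the range given in Attachment 1" |
| SAP 6.2 | ALT above 3 × ULN; Hy's Law | eligible |
| SAP 6.4 | abnormal ECG values | eligible |
| SAP 6.3, Table 4 | vital-sign abnormalities | cannot qualify, because each criterion includes a change from baseline |
| Protocol 11.3 | C-SSRS incidence and shifts | no restriction stated |
| SAP 6.6.1 | all C-SSRS summaries | subject excluded |

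Section 6.6.1 is the only row where a missing baseline removes a subject from an output that does not use the baseline.

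**The rule applied case by case**

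- No pre-treatment form, post-baseline form scored 1 to 10: excluded from every C-SSRS output, although the event was observed and scored.
- Pre-treatment form, suicide before any post-baseline form: excluded.
- Both forms, later suicide entered on a C-SSRS as 10: included and counted as behavior.
- Both forms, later suicide with no further form: the subject is included, but the maximum comes from earlier interviews unless 10 is assigned from AE or death data. The SAP does not say whether it is.
- Any of these events reported as an AE in the treatment-emergent window: counted among the suicidality TEAEs of special interest (SAP 6.1) whatever the form status. Deaths are also listed.

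**Direction of the effect.** Let N subjects with e events be kept, and m subjects with f events be excluded.

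- Reported count: e. Full count: e + f. Since f ≥ 0, the reported count can only be equal or lower.
- Reported proportion: e/N. Full proportion: (e + f)/(N + m). The reported figure is the lower one only if f/m exceeds e/N. The documents give none of these quantities, so the direction for percentages is open.

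**Size.** The documents contain no count. Purely as an assumption, 1,000 dosed subjects with 0.5% to 3% lacking a usable form would give 1,000 × 0.005 = 5 to 1,000 × 0.03 = 30 subjects excluded. Neither input comes from the documents.

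**Can a form be missing at all?** Three features make it possible:

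- Predose assessments already done on the same day in the parent study need not be repeated at entry (Time and Events footnotes), so the relevant form may sit in another study's database.
- SAP 2.2 defines baseline but not pre-treatment, and many entrants have already received esketamine. Section 6.6.1 does not say whether a parent-study form qualifies.
- Exclusion criterion 2 may be judged clinically instead of on the C-SSRS, so enrolment does not guarantee a form.

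**The case against.** The strongest reply is that little is lost. The C-SSRS is scheduled predose on Day 1 of induction and at Visit 2.1, and baseline accepts the last observation on or before the phase start. Missing baselines should therefore be uncommon. Post-baseline forms are frequent too: every induction visit, then in the first weeks of optimization/maintenance and every 2 weeks after that. This stands, and it limits the size of the point.

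The second reply is that suicidality does not rest on this table alone. The TEAE category names completed suicide, suicide attempt, suicidal behavior and suicidal ideation. It is summarized on the Full analysis sets by phase, and AEs are also summarized on the All Enrolled set for the whole treatment period. These sets require a dose, not a C-SSRS form. This also stands, so a reader should not infer that the events vanish from safety reporting. It does not cover ideation that surfaces only when the C-SSRS is asked and is never entered as an AE.

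The third reply is that the SAP is not uniform in keeping missing baselines, as Table 4 for vital signs shows. That is correct, but those criteria are defined as changes and cannot be evaluated without a baseline. The C-SSRS maximum category can be.

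**Conclusion.** The restriction in SAP 6.6.1 is broader than its purpose requires, and broader than the SAP's general rule. It removes subjects with observed post-baseline ideation or behavior from two descriptive outputs on a primary-objective item. The likely number is small and cannot be computed from the documents. This is a cheap correction to a stated exclusion rule and does not threaten the study's safety conclusions.

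Two stronger readings are tempting, and the documents do not support them:

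- *Completed suicides are excluded from the table.* They are not excluded as a class. Score 10 is a planned category, and a subject with both forms stays in. A suicide is missed only if one of the forms is absent, or if nobody records 10 after the death. On that last point the SAP is silent, and silence is not a rule of exclusion.
- *Reported incidence is biased downward.* This is true of counts in the sense that they cannot rise. For percentages it does not follow, because the denominator shrinks as well.

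The conclusion assumes that the 6.6.1 sentence is applied as written to every summary in that section.

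**What to change.** In SAP 6.6.1:

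1. Base the per-visit frequency distribution and the maximum-category summary on all subjects dosed in the phase who have any post-baseline C-SSRS.
2. Apply the baseline requirement to the shift tables only, and show subjects without a baseline there as a separate row.
3. As a secondary clarification, state how score 10 is assigned when a suicide is recorded as an AE or cause of death but no later C-SSRS form exists. One option is to derive it from the AE or death data with a footnote naming the source, so that the C-SSRS and TEAE outputs agree. Step 1 alone would not recover a death before the first post-baseline form.

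The change needs no new data. It costs a few sentences, minor reprogramming and one small derivation. Reported counts may become slightly higher, and step 3 mixes two data sources in one table, which is why the footnote is needed.

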6.6.2. Modified Observer’s Assessment of Alertness/Sedation (MOAA/S)

The MOAA/S will be used to measure treatment-emergent sedation with correlation to levels of sedation defined by the American Society of Anesthesiologists (ASA) continuum. The MOAA/S

scores range from 0 (No response to painful stimulus; corresponds to ASA continuum for general anesthesia) to 5 (Readily responds to name spoken in normal tone [awake]; corresponds to ASA continuum for minimal sedation).

The MOAA/S is measured on each dosing day every 15 minutes from predose to t=+1 hours postdose or longer, if necessary, until the subject has a score of 5.

- If the score is ≤ 3 at any time during the 1 hour postdose interval, the MOAA/S will be performed every 5 minutes until a score of 4 is reached (at which point a frequency of every 15 minutes can be resumed until t=+1 hours postdose).
- If a subject does not have a score of 5 at t=+1 hours postdose, they should continue to be monitored. For subjects with a score of 4, the assessment should be repeated every 15 minutes. For subjects with a score of ≤ 3 , the assessment should be repeated every 5 minutes until the score returns to 5 or the subject is referred for appropriate medical care, if clinically indicated.

Descriptive statistics of the MOAA/S score, changes from predose, and the proportion of subjects experiencing sedation (score less than or equal to 4) will be summarized at each scheduled time point. A bar chart over time for MOAA/S will be provided.

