		8	Week 2 (OP/MA)	2 - 11	8	
		15	Week 3 (OP/MA)	12 - 18	15	
		22	Week 4 (OP/MA)	19 - 29	22	
		22 + i*14	Week (4 + i*2) (OP/MA)	16 + i*14 to 29 + i*14	22 + i*14	
		OP/MA final visit	End Point (OP/MA)	2 to end of OP/MA		
	MOAA/S ^c (IND and OP/MA [predose and every 15 minutes to 1H]), CGADR ^d (IND and OP/MA [30M; if not “Yes”, repeat every 15 minutes until “Yes”])	IND	1	Day 1 (IND)	≤ 1	1
			4	Day 4 (IND)	2 - 6	4
8			Day 8 (IND)	7 - 9	8	
11			Day 11 (IND)	10 - 13	11	
15			Day 15 (IND)	14 - 16	15	
18			Day 18 (IND)	17 - 20	18	
22			Day 22 (IND)	21 - 23	22	
25			Day 25 (IND)	24 to end of IND	25	
IND final visit			End Point (IND)	2 to end of IND		
OP/MA i=1,2,3,...		1	Week 1 (OP/MA)	≤ 1	1	
		8	Week 2 (OP/MA)	2 - 11	8	
		15	Week 3 (OP/MA)	12 - 18	15	
		22	Week 4 (OP/MA)	19 - 25	22	
		22 + i*7	Week (4 + i*1) (OP/MA)	19 + i*7 to 25 + i*7	22 + i*7	
		OP/MA final visit	End Point (OP/MA)	2 to end of OP/MA		
Pulse Oximetry ^e (IND [predose and every 15 minutes to 1H]),		IND	1	Baseline	≤ 1	1
			4	Day 4 (IND)	2 - 6	4
			8	Day 8 (IND)	7 - 9	8

Table 1: Analysis Visits

Parameter	Analysis Phase	Scheduled Day ^a	Time Interval (label on output)	Time Interval ^a (Day)	Target Time Point ^a (Day)
OP/MA [predose, 30M, 1H])		11	Day 11 (IND)	10 - 13	11
		15	Day 15 (IND)	14 - 16	15
		18	Day 18 (IND)	17 - 20	18
		22	Day 22 (IND)	21 - 23	22
		25	Day 25 (IND)	24 to end of IND	25
		IND final visit	End Point (IND)	2 to end of IND	
	OP/MA i=1,2,3,...	1	Week 1 (OP/MA)	≤ 1	1
		8	Week 2 (OP/MA)	2 - 11	8
		15	Week 3 (OP/MA)	12 - 18	15
		22	Week 4 (OP/MA)	19 - 25	22
		22 + i*7	Week (4 + i*1) (OP/MA)	19 + i*7 to 25 + i*7	22 + i*7
OP/MA final visit	End Point (OP/MA)	2 to end of OP/MA			
Healthcare Resource Use Questionnaire (HRUQ)	OP/MA i=1,2,3,...	1	Week 1 (OP/MA)	≤ 1	1
		22	Week 4 (OP/MA)	2 - 36	22
		22 + i*28	Week (4 + i*4) (OP/MA)	9 + i*28 to 36 + i*28	22 + i*28
	OP/MA final visit	End Point (OP/MA)	2 to end of OP/MA		
PWC	OP/MA	End Point (OP/MA)	End Point (OP/MA)	1 to end of OP/MA	
	FU	7	Week 1 (F/U)	1 to 10	7
		14	Week 2 (F/U)	11 to 17	14
		21	Week 3 (F/U)	18 to 24	21
		28	Week 4 (F/U)	25 to end of F/U	28
F/U final visit	End Point (F/U)	1 to end of F/U			

^a For IND phase, time interval is relative to the first day of the induction phase.

For OP/MA phase, time interval is relative to the first day of the optimization/maintenance phase.

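### MOAA/S is summarised only at scheduled time points, so no per-session incidence, lowest score or recovery time is planned

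*SAP*

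**What the plan says.** Protocol 2.1.2 lists alertness and sedation on the MOAA/S as a safety endpoint for short-term effects on the dosing day. Scores run from 0 (deepest) to 5 (awake).

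- **Collection.** SAP Table 1 (section 2.3) gives the grid as "predose and every 15 minutes to 1H". SAP 6.6.2 adds two triggers for extra readings. Within the hour: "If the score is ≤ 3 at any time during the 1 hour postdose interval, the MOAA/S will be performed every 5 minutes". At the end of the hour: "If a subject does not have a score of 5 at t=+1 hours postdose, they should continue to be monitored". Protocol 9.2 has the same rules ("the MOAA/S will be performed every 5 minutes until a score of 4 is reached"), and SAP 6.6.2 describes measurement as running to 1 hour "or longer, if necessary, until the subject has a score of 5".
- **Analysis.** The planned outputs are descriptive statistics, change from predose and one proportion: "the proportion of subjects experiencing sedation (score less than or equal to 4) will be summarized at each scheduled time point". The only other output named is a chart: "A bar chart over time for MOAA/S will be provided". Protocol 11.3 is in line with this: "Descriptive statistics of scores and their changes (and/or percent changes) from pre-dose or baseline will be summarized at each scheduled time point".
- **End Point row.** Table 1 has an End Point row for MOAA/S. SAP 2.2 defines End Point as the last value in the phase, not the worst.
- **Extra readings.** Footnote c to Table 1 repeats the 5-minute rule but does not say how those readings are analysed.

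Nothing in either document defines a minimum score per session or per phase, an any-time incidence, or a time to recovery.

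**The concern.** Three natural questions about a sedation endpoint are how many subjects were sedated in a session, how deeply, and for how long. A table of proportions by clock time answers none of them directly.

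Subjects reach their lowest score at different times, so no single column gives the share ever sedated. The lowest score may fall at a 5-minute reading that no table uses. The grid ends at 1 hour, so recovery after that is not timed. The single cut-off at 4 or below puts a score of 4 in the same category as a score of 0.

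The SAP handles other safety measures differently. C-SSRS uses the maximum score per phase (6.6.1), ECG the maximum over scheduled and unscheduled visits (6.4), and acute hypertension is counted if it occurs at any time in the phase (6.3). MOAA/S is sampled more densely precisely when sedation appears, yet it has no worst-value rule.

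**Working it through.** The documents state no sedation rate, sample size or power for this endpoint, so there is no figure to reproduce. All rates below are assumptions.

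**1. What the time-point proportions can say.** Let p15, p30, p45 and p60 be the proportions with a score of 4 or less among the same subjects at each scheduled reading. The any-time proportion in the session satisfies

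max(p) ≤ P(any time) ≤ min(1, sum of p).

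- 10/20/20/10%: lower bound 20%; upper bound 10+20+20+10 = 60%.
- 5/10/10/5%: lower bound 10%; upper bound 5+10+10+5 = 30%.

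The lower bound is reached when everyone sedated at any reading is also sedated at the peak reading. The upper bound is reached when no subject is sedated at two readings. The tables cannot show which case applies; subject-level data can.

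**2. Do the extra readings change the incidence of 4 or less?** No. The first 5-minute reading follows a scheduled score of 3 or less, and the first reading after 1 hour follows a 60-minute score below 5. Every session with an extra reading is therefore already counted at a scheduled reading. What is missing for incidence is the any-time derivation, not the extra data.

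**3. Is non-recovery at 1 hour missing?** No. On a 0 to 5 scale, 4 or less is the same as below 5. The planned proportion at 60 minutes is the share not yet back to 5.

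**4. What the extra readings do add.** Take one hypothetical session that follows the monitoring rules:

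| Minute | 30 | 35 | 40 | 45 | 60 | 75 | 90 |
|---|---|---|---|---|---|---|---|
| Score | 3 | 2 | 2 | 4 | 4 | 4 | 5 |
| On scheduled grid | yes | no | no | yes | yes | no | no |

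The by-time table receives 3, 4 and 4. The lowest score of 2 and the return to 5 at 90 minutes do not reach it. The last-value rule would take the 5 if this were the final session of the phase, which says nothing about depth.

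**5. Illustrative simulation.** Each row has 40,000 sessions with a triangular depth curve, a normally distributed time of peak, a uniform half-width and an exponential depth. The SAP monitoring rules are applied.

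| Peak mean/SD (min); half-width (min); mean depth (points) | Largest time-point ≤4 | Any-time ≤4 | Gap (points) | Lowest score only in an extra reading* | Below 5 at 60 min |
|---|---|---|---|---|---|
| 35/10; 15–40; 1.0 | 43.5% | 55.2% | 11.7 | 14.8% | 12.6% |
| 35/15; 10–30; 1.0 | 28.8% | 52.0% | 23.2 | 16.1% | 10.3% |
| 35/15; 10–30; 0.5 | 13.8% | 27.6% | 13.8 | 6.4% | 4.6% |
| 35/10; 20–60; 1.5 | 62.0% | 68.7% | 6.7 | 13.7% | 34.5% |
| 45/15; 15–40; 1.0 | 37.8% | 54.0% | 16.2 | 20.3% | 27.8% |

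*As a share of sessions with a scheduled score of 3 or less.

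The any-time figure for 4 or less was identical from scheduled readings alone and from all readings, as step 2 requires. In most sessions with a score of 3 or less, the scheduled grid already held the lowest score.

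**The case against.** The strongest reply is that the SAP does what the protocol asks. The study is single-arm and descriptive, with no hypothesis, and sedation is not among the items singled out in the primary objective. A time-point proportion is a valid point prevalence, and nothing labels it a session rate. That stands: the planned table is not wrong, only insufficient for the questions above.

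It can also be said that the later readings belong to the schedule, since measurement continues "or longer, if necessary, until the subject has a score of 5". Table 1 labels MOAA/S by day only, so a scheduled time point might mean the dosing day. The ambiguity is real. On the day reading, however, the SAP still does not say how several readings in a day become one value.

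Other outputs touch on sedation. The discharge-readiness assessment (SAP 6.6.3) takes it into account, and durations of somnolence and related events are summarised (SAP 6.1). Neither uses MOAA/S scores or gives depth.

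The cut-off at 4 or below was a deliberate change in SAP Amendment 2, and 3 or below is a monitoring trigger, not a defined endpoint. That also stands, so the fix adds a depth split and leaves the cut-off alone.

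A reader might infer three stronger things that the documents do not support:

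- **That leaving out the extra readings hides sedated subjects.** For 4 or less it does not (step 2).
- **That sedation still present at 1 hour is invisible.** It is in the 60-minute column (step 3).
- **That incidence is understated by a known, large factor.** An assumed 10/15/10/5% with no overlap gives 40% any-time against a 15% peak, a ratio of 40/15 = 2.7. That is the worst case for that pattern; with full overlap the ratio is 1.

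**Conclusion.** The point holds in a limited form. Followed as written, SAP 6.6.2 yields point prevalences for a listed safety endpoint. It does not yield the share of subjects sedated at any time in a session, each subject's lowest score, or the time of recovery after 1 hour. The single cut-off pools all depths from 4 to 0.

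The size of any understatement is unknown. It arises only if a time-point figure is read as a session rate, and it can be nil. In the assumed scenarios the gap was about 7 to 23 percentage points for 4 or less, and the lowest score was seen only in an extra reading in about 6% to 20% of sessions with a score of 3 or less. These figures depend on the assumed curve shapes and should not be quoted as estimates for this trial.

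The change is worth making because it is cheap and matches how the SAP already treats other safety measures. The existing tables remain valid.

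**What to change.** In SAP 6.6.2:

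1. Derive the minimum postdose MOAA/S score per subject for each dosing session and each phase, using scheduled, 5-minute and beyond-1-hour readings.
2. Report the number and percentage of subjects by minimum score, at least for 4 or less and 3 or less.
3. For subjects below 5 at 1 hour, summarise the time to return to 5, and count separately those referred before reaching it.
4. State whether a scheduled time point means the clock reading or the dosing day, and what the bar chart shows.
5. Keep the by-time-point table and the bar chart.

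A per-phase minimum tends to fall as more sessions are read, so give the number of sessions behind it. The current protocol schedule marks MOAA/S only for Visits 2.1 to 2.4 of the optimization/maintenance phase, whereas SAP Table 1 continues weekly.

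The cost is a few derived variables and some SAP text. Protocol 9.1.1 already has assessment dates and times recorded, so no new data are needed. With the same denominator, the per-session rates will be equal to or higher than the time-point figures, and the report should say why.
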